## **Measures**

**(1) Posttraumatic stress (PTS)** will be assessed primarily through caregiver-report on the UCLA PTSD Reaction Index. In addition to the pre-treatment/referral and post-treatment assessments discussed above, the caregiver will complete the UCLA when presenting for the 5th treatment session (score after the first phase of treatment [sessions 1-4]) and the 9th treatment session (score after the second phase of treatment [sessions 5-8]). Thus, PTS will be assessed at four separate points in the treatment process, which will allow for a comparison of the rate of progress across the two conditions. Children will also complete the self-report version of the UCLA at each of the four assessment points. **(2) Emotional and behavioral concerns** will be assessed by caregiver-report using the Strengths and Difficulties

Questionnaire (SDQ; Goodman, 1997). As with the UCLA, the caregiver will complete the SDQ at pretreatment, during sessions 5 and 9, and at post-treatment. Children will self-report their anxiety concerns on the Screen for Child Anxiety Related Disorders (SCARED; Birmaher et al., 1999) and their depression concerns on the Mood and Feelings Questionnaire (MFQ; Angold et al., 1995) at each of the four assessment points. A research assistant will be responsible for administering measures at each assessment.

**(3) Emotion regulation** will be assessed in three ways. First, caregivers will complete the Emotion Regulation Checklist (ERC; Shields & Cicchetti, 1997) during the pre- and post-treatment assessments. Similarly, children will complete the self-report Emotion Regulation Index for Children and Adolescents (ERICA; MacDermott et al., 2010) during the pre- and post-assessments. Last, children's resting and stress reactivity respiratory sinus arrhythmia (RSA) will be assessed both pre- and post-treatment. RSA is assessed via an electrocardiogram (ECG) and is a well-established psychophysiological marker of emotion regulation (Beauchaine, 2015). RSA will be assessed with a UFI 3991/4 EIRS BioLog ambulatory physiological data recorder using disposable Ag/AgCl electrodes. Electrodes will be placed on the chest and abdomen to acquire inter-beat intervals. Placement of the electrodes will be facilitated by the research assistant conducting the assessment and the child's caregiver will be present during the application and later removal of the electrodes. The caregiver will not be present during the administration of the assessment procedures. To assess resting RSA, children will watch pre-selected television programs that are not emotionally-laden for 15 minutes. Stress reactivity will then be assessed using the Trier Social Stress Test (TSST; Buske-Kirschbaum et al., 1997; Kirschbaum et al., 1993). In addition, children will be shown a \$15 gift card to a toy or electronics store prior to beginning the TSST and told that they must achieve a satisfactory performance across the TSST tasks to earn the gift card. The gift card will be provided to all participants at the completion of the TSST. In both the resting and stressor paradigms, RSA will be sampled in 30 second epochs. [name], who will be blind to participant condition, will be responsible for editing the ECG files to remove artifacts and scoring the files using CardioEdit and CardioBatch software (Brain-Body Center, University of Illinois at Chicago, 2007). [name] is trained and certified by the developers in the use of this software. **(4) Youth perception of the caregiver** will be assessed at both the pre-treatment and post-treatment assessment sessions using the Security Scale, to determine whether participation in TF-CBT improved the youth's perception of their caregiver as a source of support. To examine potential caregiver-

related interpersonal factors on this outcome, the caregiver will complete the Experiences in Close Relationship-Revised (ECR-R) and the Caregiving Systems Scale (CSS).

**(5) Participant attrition, cancelled appointments, and missed appointments without prior notice** will be recorded to determine if the conditions differ on consistency of attending and completing treatment. **(6) Treatment satisfaction** will be assessed by caregiver and child report during the posttreatment assessment using the Youth Client Satisfaction Questionnaire (YCSQ; Shapiro et al., 1997). **(7) Ability to implement TF-CBT techniques** will be assessed in multiple ways. First, the number of sessions that are cancelled because of reasons attributable to the availability of the dog will be recorded (e.g., dog/handler illness). Second, the clinician will complete a fidelity checklist after each session to report whether the assigned techniques for the session were successfully completed (see attached). Completing such checklists will allow for a comparison between the two conditions to determine whether the presence of the dogs facilitated a greater rate of completion of assigned techniques or hindered completion of assigned techniques. Third, clinicians will report whether a treatment disrupting event attributable to the dog occurred during session (e.g., emotional distress requiring handler intervention). **(8) Stress response in dogs** will be evaluated using physiological and behavioral measures. To measure hypothalamic-pituitary-adrenal (HPA) response, three saliva samples for cortisol assessment (pre-session/prior to meeting child, post-session/immediately after separation from child, and 20 minutes post-session) will be taken from each dog at treatment sessions 1, 6, and 12 (beginning of treatment protocol, predicted child peak emotional level during protocol, end of treatment protocol). Each of these samples will be obtained by the handler. Representative control day samples (at the same time on non-therapy days) will be taken by the handler at home for each dog. [name] will train handlers in the collection, transportation, and storage of samples. For autonomic nervous system response, canine heart rate will be measured at each session using a Polar H7 monitor with bluetooth connection to a tablet computer. Using conversion software, RSA (R-R intervals) will be determined for each session. Sessions will be videotaped and [name] will code behavioral stress signals in the dogs as well as children's behavior toward the dogs (Dreschel & Granger, 2005). In addition, handlers will be trained by [name] to assess their dogs' behavior before, during, and after treatment sessions using the Behavioral Instrument for the Assessment of Dog Well-Being Before/During/After Therapy Sessions (Fine, et al., 2013; Ng et al., 2015).

**(9) Stress experienced in session** will be assessed via ECG. Children will be connected to a UFI 3991/4 EIRS BioLog ambulatory physiological data recorder using disposable Ag/AgCl electrodes prior to the start of treatment sessions 1, 4, 6, 8, and 12. Placement of electrodes will be performed by a research assistant using the procedures specified previously. Event marks will be recorded at the point of transition from the 10-minute

relaxation/pleasurable activities time to the start of the implementation of techniques. RSA will be sampled in 30 second epochs and calculated for each of these two time periods (10 minute phase prior to technique implementation, 45 minute phase of technique implementation). This methodology will allow for assessment of within-participant RSA trajectories over the course of treatment, and between-group comparisons on physiological stress response both prior to and during technique implementation. **(10) Quality of therapeutic rapport** will be assessed via child and caregiver-report using the appropriate versions of the Therapeutic Alliance Scale for Children-Revised (TASC-R; Accurso et al., 2013; Creed & Kendall, 2005; Shirk & Saiz, 1992). AAT is believed to facilitate the development of rapport and, therefore, assessing rapport at multiple points in the first phase of treatment is appropriate. As such, rapport will be assessed at the 2nd and 4th treatment sessions as well as at post-treatment. A research assistant will administer the TASC-R with caregivers and children during these sessions and will explicitly state that the clinician will not be made aware of the answers provided. **(11) Attitudes toward pets** will be assessed for the youth at the pre-treatment assessment only using the Pet Attitude Scale to determine whether pre-existing attitudes toward pets is related to outcome in the TF-CBT+AAT group. **(12) The demographics** form will be completed at the pre-treatment assessment only.

**Note on the Recording of sessions:** The TLC Clinic currently has video recording capabilities and uses them on a regular basis. These recording are done by equipment installed in the TLC Clinic by the PSHMC IT department and stored digitally on PSHMC servers behind the firewall. A back-up system uses a camcorder within the clinic and the files are stored on a memory card. The files are then transferred to the TLC Clinic shared drive that is only accessible to TLC Clinic staff with permission to access the drive. The video recorded files are then deleted from the memory card.

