Susquehanna Service Dogs (SSD), a fully accredited member of Assistance Dogs International (ADI), will partner in the completion of this project (see letter of support from [name]). SSD facility dogs are fully trained/certified according to ADI standards and serve in canine-assisted interventions in local mental health settings. These dogs are skilled in basic obedience, maintain a calm manner and good social behavior in a variety of environments, and are trained for public access (<http://www.assistancedogsinternational.org/standards/assistance-dogs/standards-for-dogs/training-standards-for-facility-dogs/>). Three pre-determined facility dog/handler teams will participate in this project. Each team will schedule 4-hour blocks of time either in the morning or afternoon on various days of the week. Children assigned to the TF-CBT+AAT condition will be scheduled in one of these time blocks. The dog will then be considered an extension of the clinician; if the dog cannot attend an appointment then the appointment will be re-scheduled. This will assure that the child remains with the same dog each session for the duration of the protocol. Dogs will only be scheduled to participate with one child per day. If the child needs to change the regular appointment time, the dog's handler will be consulted and attempts will be made to re-schedule without changing the dog involved.

Having the dog's handler in the treatment room for the TF-CBT+AAT condition creates a significant confound as a second individual will not be present in the TF-CBT condition. Therefore, SSD handlers will deliver a 3-hour training to the clinicians in the management of the service dog and provide a further 7 hours of consultation to the clinicians throughout the project. When the session is ready to begin, the handler will transfer the handling duties to the clinician. Handlers will observe sessions through a

one-way mirror and/or closed circuit television system with a focus on monitoring the well-being of the dog. Handlers will be free to interrupt sessions if they believe it is warranted given the dog's behavior. Handlers will not be able to hear what is being discussed from the observation room, although various emotional responses will be visible and they may become aware of some details of the child's maltreatment. The clinicians will provide a 3-hour training to the handlers on secondary trauma and self-care, and provide continuing support to the handlers as needed.

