## 5.2 Statistical methods

Intent-to-treat analyses will be used for all statistical analyses (i.e., all of the available data from randomized participants are utilized for analyses). Descriptive statistics (e.g., means, ranges, standard deviations) will be computed for continuous variables; frequencies will be calculated for

categorical variables. Measurements of PTS, emotional and behavioral concerns, and emotion regulation are continuous variables and will be examined over time with individual-level graphical checks. Transformation methods may be needed based on normality checks (i.e., Shapiro-Wilks test). To adjust for potential confounding variables that may be identified (e.g., gender, age, number of trauma types endorsed on the UCLA), multilevel models with partial nesting (i.e., youth in the TF-CBT+AAT group nested by dog, youth in the TF-CBT group not nested) will be employed to investigate the temporal trend and compare the trajectories of outcomes between the two groups using SAS PROC NL MIXED v. 9.4. Note that parameter estimates will be obtained using maximum likelihood estimation, and that p-values can be computed based on Chi-square tests (Liang & Zeger, 1986). If missing data or dropouts occur, the mechanism (i.e., missing completely at random, missing at random) will be explored and adjusted for valid statistical inference.

Analyses of categorical data (i.e., participant attrition, cancelled appointments, missed appointments without prior notice, and ability to implement TF-CBT techniques) will likely utilize descriptive and non-parametric methods (e.g., Fisher's exact tests). Differences between the conditions for treatment satisfaction will be examined with parametric (e.g., between groups t-tests) or non-parametric

analyses (Wilcoxon rank-sum tests). Given the small sample sizes and primary interest in a covariate effect, generalized estimating equations (GEE) can be used for the analysis of repeated cortisol assessments (Wang & Long, 2011). The GEE model with autoregressive (AR) working correlation structure can be fitted to investigate the difference of within session samples and between the treatment and control day samples. Three variables of interest are included: day of sample (0 = control; 1 = treatment), the session status (0 = pre-session; 1 = post-session; 2 = 20 minutes post-session), and their interaction.

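### In-session disruptions are recorded only when put down to the dog, so their rate cannot be compared between the arms

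*Combined protocol and SAP*

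**What the plan says.** Measure (7) in the protocol's Measures section concerns whether TF-CBT can be delivered as intended. It has three components.

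- Dog-related cancellations: "the number of sessions that are cancelled because of reasons attributable to the availability of the dog will be recorded".
- A fidelity record: "the clinician will complete a fidelity checklist after each session to report whether the assigned techniques for the session were successfully completed". Its stated use is a comparison of the two conditions, to learn "whether the presence of the dogs facilitated a greater rate of completion of assigned techniques or hindered completion of assigned techniques".
- Disruptions: "clinicians will report whether a treatment disrupting event attributable to the dog occurred during session (e.g., emotional distress requiring handler intervention".

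Section 4.2 adds that "Handlers will be free to interrupt sessions if they believe it is warranted given the dog's behavior". Handlers are there to watch the dog, so this can happen only in TF-CBT+AAT sessions. Children in the TF-CBT arm may bring a stuffed animal or similar object instead.

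The Statistical methods section handles measure (7) together with attrition and attendance: "missed appointments without prior notice, and ability to implement TF-CBT techniques) will likely utilize descriptive and non-parametric methods (e.g., Fisher's exact tests". It does not treat the three components separately.

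**The concern.** The cause is part of the event definition. A TF-CBT session that stops because the child becomes distressed during the trauma narrative is not an event on this item. The same stop in a TF-CBT+AAT session counts only if the clinician puts it down to the dog.

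A dog could plausibly act in both directions. It may add interruptions, and it may prevent others by settling the child during exposure work. The net effect needs both, and this item can show only the first. Any event in the TF-CBT+AAT arm looks like an excess over a comparator that could never have had one. Conversely, distress that the dog did contribute to, but that the clinician does not attribute to it, is missed by this item. The attribution is made by the treating clinician, who knows the condition and has taken over handling the dog.

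The trial is intended to inform a larger one. Whether the dog disrupts or steadies exposure-based sessions is a natural feasibility question for that purpose.

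**Working it through.** The plan states no rate, sample size or power for disruptions, so there is no figure of its own to reproduce. The check has three parts.

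**1. Which measures can be non-zero in both arms?**

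| Measure | TF-CBT | TF-CBT+AAT | What it captures |
|---|---|---|---|
| Dog-related cancellations | zero by definition | yes | sessions not held |
| Fidelity checklist, each session | yes | yes | completion of techniques |
| Dog-attributed disruption | zero by definition | yes | events, one cause only |
| In-session RSA (sessions 1, 4, 6, 8, 12) | yes | yes | child physiology, 5 of 12 sessions |
| Attrition, cancelled and missed appointments | yes | yes | attendance |

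No row is a count of in-session disruptions from any cause.

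**2. What would a between-arm test of the disruption item show?** Inputs from the plan are 60 children, equal allocation (30 per arm) and 12 sessions each, so 30 × 12 = 360 planned sessions per arm. The number of affected children, k, is assumed. With 0/30 fixed in TF-CBT and k/30 in TF-CBT+AAT, the observed table and its mirror image are the two most extreme, so the two-sided Fisher p = 2 × C(30,k) / C(60,k).

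- k = 5: 2 × 142,506 / 5,461,512 = 0.052
- k = 6: 2 × 593,775 / 50,063,860 = 0.024
- k = 7: 2 × 2,035,800 / 386,206,920 = 0.011

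Suppose 8 of 30 children in each arm had at least one disrupted session, and 6 of the 8 in TF-CBT+AAT were put down to the dog. All-cause recording would give 8/30 against 8/30, p = 1.0. The planned item would give 0/30 against 6/30, p = 0.024.

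How often k reaches 6 depends on the true child-level rate of dog-attributed events. The binomial probability of 6 or more among 30 is 0.07 at a rate of 10%, 0.57 at 20% and 0.92 at 30%.

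**3. What would an all-cause item deliver at this sample size?** Power of Fisher's exact test at two-sided 0.05 with 30 per arm, under assumed child-level rates:

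- 20% against 40%: 0.30
- 10% against 30%: 0.37
- 20% against 50%: 0.60

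Precision, for 8/30 in each arm: standard error = √(2 × 0.267 × 0.733 / 30) = 0.114, so the approximate 95% interval for the difference is ± 1.96 × 0.114, or about ± 22 percentage points. The comparison can be estimated, but imprecisely.

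**The case against.** The strongest reply is that the plan already has a two-arm, two-directional measure. The fidelity checklist is completed after each session and is expressly meant to show whether the dogs helped or hindered. A session broken off during the narrative would register in either arm if the assigned technique was left unfinished. In-session RSA adds "between-group comparisons on physiological stress response both prior to and during technique implementation", and attendance data "will be recorded to determine if the conditions differ on consistency of attending and completing treatment". A reader might infer from the disruption item that the trial can say nothing about whether the dog makes sessions more or less disrupted. The documents do not support that, because these measures bear on the question.

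They are, however, indirect. A session can be interrupted and still complete its techniques, or leave techniques undone without any interruption. RSA covers 5 of 12 sessions and records physiology, not events. Attendance concerns sessions not held. None gives a disruption rate.

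Three further objections stand in full.

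- A reader might call this the trial's only adverse-event record, or a failed safety comparison. The protocol files it as a feasibility item, and counting problems caused by the added component is a legitimate one-arm measure. The text supplied for review is also incomplete: the attached checklist form is not included, so it may already have a field for interruptions.
- A reader might infer that the plan will test this item against zero. It does not commit to that: the wording is tentative, descriptive reporting is allowed, and the between-condition comparison is tied explicitly only to the checklist. The Fisher values show what a misuse would produce, using assumed counts.
- An any-cause comparison would have low power, so the gain is mainly descriptive.

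**Conclusion.** The point holds in a limited form. As described, the disruption item is zero by definition in TF-CBT, so it supports no between-arm comparison of disruption rates, and the analysis section does not set it apart from the parts of measure (7) that do have a comparator. The fidelity checklist and RSA give indirect evidence on net disruption but cannot supply the missing rate.

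The risk is one of misreading: about six affected children in TF-CBT+AAT would be enough for a nominally significant result that says nothing about net disruption. That size rests on 30 children analysed per arm, a child-level test and assumed counts. The conclusion also assumes that the attached checklist has no any-cause interruption field. If it has one, only the analysis wording needs changing.

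Severity is low to moderate. This is a feasibility outcome, not the primary one, and the change is a cheap improvement.

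**What to change.** - On the after-session checklist that clinicians already complete in both arms, add one yes/no item: was the session interrupted, paused or ended early for any reason? Follow it with a cause field: child distress, dog or handler, caregiver, other.
- In the Statistical methods section, compare all-cause disruptions between arms as an estimate with a confidence interval. Take the child as the unit (at least one disrupted session), or allow for repeated sessions within a child. State that the estimate will be imprecise at 30 per arm.
- Report dog-attributed disruptions and dog-related cancellations descriptively in TF-CBT+AAT only, with no between-arm test.

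The cost is a few seconds of entry per session. The information now planned is kept, and neither the treatment nor the sample size changes. One weakness remains: the cause field still depends on a clinician who knows the condition. The any-cause item avoids the attribution step, although it too is reported by that clinician.

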Modified variance estimators are calculated to reduce bias when sample sizes are small and t-tests are used for valid inference. The analysis will be conducted using the function of “geesmv” in R (Wang et al. 2016). Similar methods can be used for the analysis of canine heart rate variability and behavior.

With regards to the ECG data, interrupted time series analyses can be used to analyze RSA from two time periods. The covariates of interest include time (in minutes) since the start of RSA assessment, the treatment group (0 = TF-CBT; 1 = TF-CBT+AAT), the time period (0 = phase prior to

technique implementation; 1 = technique implementation), time (in minutes) since technique implementation, and the interactions of the last variables with the treatment group. The correlation among time series observations is represented in the error term. Residual plots can be used to detect the autocorrelation, where the Durbin–Watson statistic can be used. This model can be fitted by SAS PROC AUTOREG v. 9.4. Regression-based mediational analyses can be conducted at each of the four assessment sessions to examine if therapeutic rapport mediates the relationship between the presence of the dogs and PTS outcomes. Bootstrap or Monte Carlo methods can be applied to testing significance of the indirect effect (Tofighi & MacKinnon, 2015). This model can be fitted using the PROCESS macro for SAS v. 9.4 (Hayes, 2013).

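### In-session RSA is to be followed across sessions 1, 4, 6, 8 and 12, but the only model named for it has no session term, so the trajectory over treatment and any arm difference in it are not estimated

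*Combined protocol and SAP*

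**What the plan says.** Measures item (9), under 4.2 Study Procedures, has children connected to the ECG recorder "prior to the start of treatment sessions 1, 4, 6, 8, and 12". Within each of those sessions, "RSA will be sampled in 30 second epochs and calculated for each of these two time periods": the 10 minutes before techniques begin and the roughly 45 minutes of technique work. The item then gives two uses for the data. One is across sessions: "This methodology will allow for assessment of within-participant RSA trajectories over the course of treatment". The other is between arms, by phase: "between-group comparisons on physiological stress response both prior to and during technique implementation".

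The analysis is in 5.2 Statistical methods, which says that "interrupted time series analyses can be used to analyze RSA from two time periods". On the terms, "The covariates of interest include time (in minutes) since the start of RSA assessment, the treatment group", followed by the period indicator, "time (in minutes) since technique implementation, and the interactions of the last variables with the treatment group". Correlation is placed in the error term, and PROC AUTOREG is the named procedure.

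The same section has a multilevel model that compares outcome trajectories between the arms. The continuous outcomes it names are posttraumatic stress, emotional and behavioral concerns, and emotion regulation, which are items (1) to (3) of the Measures. In-session stress, item (9), is not among them.

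**The concern.** The two sections use time in different senses. In Measures item (9), the course of treatment is indexed by session number. In the ECG model, both time variables are minutes within a recording, and the other terms are period and group. Nothing in the model says which of the five sessions an observation came from, and no rule says how the sessions are to be combined.

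This matters because the protocol itself expects the sessions to differ. Treatment runs through skills-building (sessions 1 to 4), exposure (5 to 8) and mastery (9 to 12), so the five recorded sessions fall in all three phases. Measures item (8), in setting the dogs' cortisol sampling, takes session 6 as the predicted peak of the child's emotional level. An effect of the dog that builds, fades or is confined to the exposure phase is plausible on the protocol's own account. Section 5.2 on sample size also makes effect-size estimates for a larger trial a primary objective, and for that it helps to know whether an effect is constant or changing.

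**Working it through.** **The plan's own figure.** The documents give no RSA variance, target effect or power. Their only computed figure concerns the UCLA score. With 30 per arm, SD 6.5 and two-sided 0.05 (sidedness assumed), the detectable difference at 80% power is 6.5 × √(2/30) × (1.960 + 0.842) = 4.70 points. That agrees with the stated figure of about 5. Nothing below depends on it.

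**The listed model.** Let *t* be minutes since recording began, *G* the arm, *P* the period and *T* minutes since techniques began. Reading the listed interactions as those of *P* and *T* with *G*:

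RSA = b0 + b1·t + b2·G + b3·P + b4·T + b5·P·G + b6·T·G + error

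That is seven coefficients, none indexed by session. The data would be (10 + 45) × 2 = 110 epochs per session and 110 × 5 = 550 per child.

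**Reading 1: sessions pooled.** With all five sessions recorded, each carries equal weight.

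- *Growing difference*, 0 at session 1 to D at session 12: d(s) = D(s − 1)/11. At sessions 1, 4, 6, 8 and 12 this is 0, 3/11, 5/11, 7/11 and 11/11 of D. The mean is (26/11)/5 = 26/55 = 0.473D.
- *Crossing difference*, −D/2 to +D/2: the mean is 0.473D − 0.5D = −0.027D, close to zero.

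A noise-free check shows the same thing with assumed values. The mean session number is 31/5 = 6.2. Data set A is RSA = 6 − 0.5P + 0.2G. Data set B adds 0.1 × (s − 6.2) × G, so its arms diverge by 0.1 units per session. The listed model returned the same coefficients for both: 6, 0, 0.2, −0.5, 0, 0, 0. With session and session-by-group added, the session-by-group coefficient was 0 for A and 0.1 for B.

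**Reading 2: one fit per session.** This gives five sets of seven coefficients and five group contrasts in order. They can be looked at side by side, but no term or contrast tests whether they differ.

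**Does another analysis cover it?** The multilevel trajectory model includes emotion regulation, and item (3) does count RSA as a marker of that. But item (3)'s RSA is the resting and stress-test recording made before and after treatment. The in-session recording is a separate item, and 5.2 sends its two-period data to the time-series model.

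**Linear or categorical session?** Suppose the arm difference is D at sessions 4, 6 and 8 and zero at 1 and 12. Session numbers centred at 6.2 are −5.2, −2.2, −0.2, 1.8 and 5.8, with sum of squares 27.04 + 4.84 + 0.04 + 3.24 + 33.64 = 68.8. The fitted linear slope of the difference is D(−2.2 − 0.2 + 1.8)/68.8 = −0.009D per session, which is nearly flat. A linear arm-by-session term would miss a mid-treatment effect, so session should be a five-level factor. The arm-by-session test then has (2 − 1)(5 − 1) = 4 degrees of freedom.

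**The case against.** The strongest reply is that the plan is unspecific rather than wrong. It says the time-series method can be used and that the covariates include those listed, so a session term is not ruled out. That is fair, and the two sections do not contradict each other. But no session-level analysis is named anywhere, so any trajectory analysis would have to be chosen later, possibly after the data are seen.

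A reader might infer that item (9) defines the measure as a trajectory, or that it asks outright whether the arms diverge over treatment. It does neither. The trajectory is one of two stated uses. The between-arm comparison is stated separately and by phase, and the time-series model addresses it. Divergence between arms combines the two uses. Even on the narrow reading, the within-child trajectory is still not estimated.

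A reader might also infer that the trial would report no physiological effect when there is one. The documents do not support that. Averaging or cancellation arises only if the sessions are pooled, which the plan does not say. Fitted session by session, a growing or reversing difference would be visible, though untested.

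Nor can a power figure be put on the loss. The documents give no RSA variance, no session-to-session correlation and no child-to-child variation in change. Comparing simpler tests under assumed values would not represent the epoch-level model that is planned.

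Finally, this is one of twelve measures, and the sample size rests on another. That limits the weight of the point but does not remove it.

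**Conclusion.** The point stands in this form: one of the two stated uses of the in-session RSA data has no analysis. Under the listed terms, neither the trajectory across sessions 1, 4, 6, 8 and 12 nor its difference between arms is estimated. This follows from the text and needs no assumption about RSA.

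The size is conditional. If the sessions are pooled with equal weight, a linearly growing difference is reported at 0.47 of its final value and a symmetric crossing difference at about −0.03 of its range. If they are analysed separately, there is no dilution, but also no test of change. The point is about which quantity is estimated, not about its standard error. It warrants a correction to the plan for a secondary measure and does not touch the UCLA analysis.

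**What to change.** In the ECG paragraph of 5.2 Statistical methods, add a second model for item (9):

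- **Outcome:** mean RSA per child for each period at each of sessions 1, 4, 6, 8 and 12.
- **Fixed effects:** arm, session (categorical, five levels), period, arm-by-session and arm-by-session-by-period, with the remaining two-way terms that the three-way term implies.
- **Random effects:** a child-level effect, and the same partial nesting by dog that the section already sets for the other outcomes.
- **Named test:** arm-by-session, averaged over the two periods, as the test of whether the RSA trajectory over treatment differs by arm. Report the estimated mean for each arm at each session with its interval.

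Keep the within-session time-series model for the by-phase comparison of the arms, and state whether it pools the sessions or is fitted to each. If the sponsor does not want a trajectory analysis, the alternative is to delete that use from Measures item (9).

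The cost is SAP wording and one more model on data already planned. The drawback is one more secondary test. With 4 degrees of freedom and 30 children per arm its power is likely to be modest, and it cannot be calculated from the documents, so the session-by-session estimates should carry most of the interpretation.
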